4.4.2.1. Capillary Leak Syndrome

In addition to the summaries described in [Section 4.4.2](#), summaries will be provided that include:

- Summary of number of CLS events, exposure to tagraxofusp prior to onset of CLS, and time to first onset and time to resolution of CLS events;
- Summarized incidence of albumin infusions and timing of infusions in relation to CLS onset;
- Plots of liver function and albumin laboratory values over time for patients who experience CLS;
- Comparison of demographic characteristics of patients who experience AESI of CLS to those who do not

Additionally, analyses of capillary leak syndrome will be provided based on an FDA algorithm, found in [Section 8.3](#).

4.4.3. Laboratory Data

Clinical laboratory values will be expressed in Système International (SI) units.

The actual value and change from baseline (Day 1) to each on-study evaluation through cycle 6 will be summarized for each clinical laboratory parameter, including hematology, clinical chemistry, coagulation, and urinalysis. In the event of repeat values, the last non-missing value per study day/time will be used.

[figure not shown]
Shift tables of change in CTCAE grade of laboratory parameters from baseline to worst value and from baseline to last value on study will be presented. Both scheduled and unscheduled visits will be included in shift tables.

To assess for possible drug-induced liver injury (DILI) (FDA 2009), a figure plotting peak alanine aminotransferase (ALT) versus peak total bilirubin (both on a logarithmic scale \times upper limit of normal [ULN]) will be produced similar to that recommended by Watkins et al (Watkins, et al. 2008) so that values within the normal reference range (<ULN) for ALT and total bilirubin are found in the left lower quadrant and Hy's Law case candidates are in the upper right quadrant (ALT $>3 \times$ ULN and total bilirubin $>2 \times$ ULN). Patients with Gilbert's syndrome or cholestasis are typically found in the upper left quadrant, and patients with ALT elevations without significant hepatic abnormality (ie, without increased total bilirubin) are found in the lower right quadrant. The peak total bilirubin value plotted will be the peak within ± 7 days of the peak ALT value. If at least five patients are identified as potential Hy's Law Cases, a summary table will be produced for the number and percentage of patients who have values of AST (>3 to $\leq 5 \times$ ULN, >5 to $\leq 10 \times$ ULN, >10 to $\leq 20 \times$ ULN, $>20 \times$ ULN), ALT (>3 to $\leq 5 \times$ ULN, >5 to $\leq 10 \times$ ULN, >10 to $\leq 20 \times$ ULN, $>20 \times$ ULN), ALP ($>1.5 \times$ ULN), or TBL (>1.5 to $\leq 2 \times$ ULN, $>2 \times$ ULN) after initiation of study drug. In this table, a patient may be counted only one time. For instance, a patient with a result of AST of $11 \times$ ULN will be counted in the category of >10 to $\leq 20 \times$ ULN.

This plot will be repeated for peak aspartate aminotransferase (AST) by total bilirubin.

An example of the scatterplot is provided in [Figure 4-1](#).

Figure 4-1: Hy's Law Candidates Scatterplot

Time to first onset of elevated AST and ALT will be analyzed using Kaplan-Meier analyses and be presented as figures.

All laboratory data will be provided in by-patient data listings.

A by-patient listing will also be presented for all laboratory values with CTCAE Grade ≥ 3 .

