Hypoalbuminemia (any Grade = 58.7%; Grade ≥ 3 = 0%) and transaminase elevation (any Grade = 50%; Grade ≥ 3 = 25%) were the most common Grade ≥ 3 AE attributed to SL-401, however almost all episodes were transient. Time courses of liver function tests (LFTs) and albumin among the patients treated with Regimen B indicate that LFT elevations tended to peak approximately two weeks after the first infusion of SL-401, while albumin levels, supported by the administration of albumin to patients with serum albumin falling below 3 g/dL, reached a minimum approximately one week after the first infusion. In most cases, levels of the laboratory parameters resolved to near baseline levels by 14-28 days after the first infusion. Other AEs commonly (i.e., any Grade in $\geq 15\%$ of patients) attributed to SL-401 included fever (any Grade = 29.3%; Grade ≥ 3 = 1.1%), hypocalcemia (any Grade = 25.0%; Grade ≥ 3 = 0%), edema (any Grade = 18.5%; Grade ≥ 3 = 3.3%), and nausea (any Grade = 16.3%; Grade ≥ 3 = 0%).

A single cycle of SL-401 was associated with single agent activity in patients with R/R AML, including 2 durable CRs of 8 and >25 months duration and 5 partial responses (PRs). OS also appeared to be improved among the most heavily pretreated AML patients compared with historical survival results. Specifically, in AML patients who had progression through at least two previous therapies (i.e., third-line or greater; n = 35), the median OS was 3.6 months, more than double the historical median OS of 1.5 months ([Giles et al. 2005](#)). Multiple durable

objective responses were also observed among the patients with BPDCN. Among 9 BPDCN patients treated with 12.5 µg/kg/day who were evaluable for response, there were 5 CRs (durations of 3, >3, 5, >7, and >20 months) and 2 PRs yielding a response rate of 78% (two patients treated with 12.5 µg/kg/day and one patient treated with 9.4 µg/kg/day were not evaluable for response).

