9.3.5 Study Day 21 \pm 7 Days: End of Cycle

Note: The end-of-cycle evaluations (Day 21 or thereafter) may also serve as the pre-infusion evaluations for the subsequent cycles; with the exception of vital signs, these do not need to be duplicated on successive days unless there is an abnormality or other clinically relevant reason for repeat evaluation.

All Patients, All Study Stages:

- Concomitant medication assessment
- ECOG performance status
- Physical examination
- Vital signs and weight
- 12-lead ECG
- Clinical laboratory tests: hematology, serum electrolytes and chemistry (including albumin), coagulation parameters, and urinalysis
- Tumor response assessment: bone marrow aspiration (\pm biopsy) and peripheral blood sample (AML and BPDCN). If the Cycle 1 (Day 21 [\pm 7]) bone marrow examination is empty (i.e., hypocellular) or inadequate, a bone marrow examination should be repeated in 7 (\pm 7) days to document response. If additional time is required to complete the repeat examination, consult with the Medical Monitor. If CD123 flow cytometry or IHC stain was performed on the bone marrow aspirations (\pm biopsy), then the results should be recorded in the eCRF.

- Collection of peripheral blood (serum) for immunogenicity
- Monitoring for changes in visual acuity and color vision
- AE and SAE monitoring

Patients with BPDCN Only:

- Tumor response assessment: skin, including mSWAT

9.3.6 Study Day 28 \pm 3 Days, Then Every 7 \pm 3 days: Delayed End of Cycle for Toxicity Resolution Only if Required**All Patients, All Study Stages:**

- Concomitant medication assessment
- ECOG performance status
- Vital signs and weight
- 12-lead ECG
- Clinical laboratory tests: hematology, serum electrolytes and chemistry (including albumin), coagulation parameters, and urinalysis
- AE and SAE monitoring

9.4 Cycles 2 – 6

Note: The end-of-cycle evaluations (Day 21 or thereafter) may also serve as the pre-infusion evaluations for the subsequent cycles; with the exception of vital signs, these do not need to be duplicated on successive days unless there is an abnormality or other clinically relevant reason for repeat evaluation.

9.4.1 Days 1 – 5 (Up to Day 10 if Infusion(s) Held): Pre-Infusion**All Patients, All Study Stages:**

- Inpatient admission (Day 1) or treatment at a suitable outpatient facility
- Vital signs and weight
- AE and SAE monitoring

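### SAP 4.4.3 looks for Hy's Law candidates only around each patient's single highest ALT or AST, and no planned output tabulates joint enzyme and bilirubin elevations

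*SAP*

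**What the plan says.** SAP 4.4.3 plans "a figure plotting peak alanine aminotransferase (ALT) versus peak total bilirubin", both as multiples of ULN. The bilirubin value is not the study-wide maximum. It is tied to one date: "The peak total bilirubin value plotted will be the peak within ± 7 days of the peak ALT value". With limits of ALT >3×ULN and total bilirubin >2×ULN, "case candidates are in the upper right quadrant", while "patients with ALT elevations without significant hepatic abnormality (ie, without increased total bilirubin) are found in the lower right quadrant". The same plot is made for AST.

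The summary table is conditional: "If at least five patients are identified as potential Hy's Law Cases, a summary table will be produced". The pool in which the five are counted is not stated. The table has separate bands for AST, ALT, ALP and total bilirubin, and no row combines an enzyme with bilirubin.

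Other liver outputs have no minimum count:
- CTCAE shift tables to worst value, by parameter, and Kaplan-Meier figures of time to first AST or ALT elevation (SAP 4.4.3).
- By-patient listings of all laboratory data and of Grade ≥3 values (SAP 4.4.3).
- AESI tables for possible drug-induced liver injury, and AE incidence by cycle (SAP 4.4.2).

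**The concern.** Protocol 6.2 sets a 21-day cycle and Protocol 7.5.2 sets no maximum duration, so a patient can have many separate opportunities for an enzyme elevation. A rule that looks at bilirubin only around the highest one cannot see a joint elevation elsewhere. It then places the patient in the quadrant that the SAP associates with ALT elevation and no increase in bilirubin.

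Transaminase elevation was the most common TEAE in the July 2016 BPDCN data (ALT increased in 62% and AST increased in 58% of 26 patients; Protocol 3.7.2). When enzyme rises are that frequent, a concurrent bilirubin rise is the feature that separates a possible serious liver injury from the rest. Drug-induced liver injury is also a listed AESI. At stake is whether the report can state how many patients met both limits together.

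**Working it through.** The documents give no error rate or expected count for this rule, so there is no figure to reproduce. I applied the rule as written.

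**1. A patient the rule misses (illustrative values).**
- Cycle 1 Day 15 (study Day 15): ALT 8×ULN, bilirubin 1.0×ULN.
- Cycle 3 Day 15 (study Day 2×21 + 15 = 57): ALT 4×ULN, bilirubin 2.6×ULN.

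The peak ALT is 8 on Day 15 and the window is Days 8 to 22. Day 57 is 42 days away, so the plotted point is (8.0, 1.0), lower right. Yet on Day 57, 4 > 3 and 2.6 > 2 hold together.

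**2. General condition.** Let A be ALT at the qualifying elevation (A > 3) and A_max the study peak. Since A_max ≥ A > 3, the point always lies on the right. It is upper right if bilirubin within ±7 days of the peak exceeds 2×ULN, and the patient is then correctly flagged. Otherwise it is lower right and the patient is missed. The AST plot recovers the patient only if peak AST exceeds 3×ULN and falls within 7 days of a bilirubin value above 2×ULN.

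**3. What the window covers.** Protocol 7.5.4 schedules chemistry on Days 1–5, 8, 15 and 21, which is 8 visits per cycle and 48 over six cycles. In the earlier single-cycle study, "LFT elevations tended to peak approximately two weeks after the first infusion of SL-401" (Protocol 3.7.1), which suggests Day 15.
- Peak on Day 15: Days 8, 15, 21 and the next cycle's Day 1 (Day 22) are inside, 4 of 48.
- Peak on Day 8: Days 1–5, 8 and 15 are inside, 7 of 48, none from another cycle.
- Within one cycle, an ALT peak on Day 8 and a bilirubin peak on Day 21 are 21 − 8 = 13 days apart. The Day 21 value is excluded even if ALT is still above 3×ULN.

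The 15-day window is 15/42 = 36% of two cycles and 15/126 = 12% of six.

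**4. The five-patient condition.** As a share of possible pools, five is 5/42 = 11.9% of treated Stage 4 patients (SAP 1.1), 5/95 = 5.3% of the approximate BPDCN cap and 5/145 = 3.4% of the approximate study cap (protocol synopsis). The candidate rate p is not in the documents, so the values below are assumptions.

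P(1 to 4 cases) = Σ (x = 1 to 4) C(N,x) pˣ(1−p)^(N−x)

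| N | p = 1% | p = 2% | p = 5% | p = 10% |
|---|---|---|---|---|
| 42 | 0.34 | 0.57 | 0.83 | 0.58 |
| 95 | 0.61 | 0.81 | 0.47 | 0.03 |
| 145 | 0.75 | 0.78 | 0.14 | 0.00 |

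These are the chances that candidates exist but the table is not produced, assuming every candidate is identified. The two rules compound, because a candidate missed at step 2 does not count toward the five.

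**5. Does another output give the joint count?** Shift tables and onset figures treat each test separately. Listings are not summarised. AESI tables depend on an event having been reported as an AE. Even when produced, the conditional table has no joint row. None of them tabulates concurrent elevations.

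**The case against.** The strongest reply is that this is a descriptive screening plot modelled on a published method, with no bearing on efficacy or formal inference, and that the surrounding outputs are substantial. One to four identified candidates would still be visible as points on the plot and in the listings, and would be in the AESI tables if reported as AEs. AE incidence by cycle, including Grade ≥3, would show repeat-cycle enzyme events. All of this stands, and it means identified cases do not disappear from the report. It does not supply a joint count, and it does not identify a candidate whom the plot puts in the wrong quadrant.

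Three stronger readings are tempting, and the documents do not support them.
- **Enzymes rise again in every cycle, so a large share of candidates is lost.** If a patient had k elevated cycles and bilirubin were equally likely to rise in any one of them, the rule would miss (k−1)/k: half for k = 2, three quarters for k = 4. No section reports recurrence by cycle. The Protocol 3.7.1 timing comes from a single-cycle study, Protocol 3.7.2 calls the elevations largely transient, and Protocol 3.8 says most Stage 1 patients could receive multiple cycles despite Cycle 1 elevations. If bilirubin rises with the highest ALT, the loss is zero.
- **The ±7-day window does not fit the visit schedule.** For a Day 15 peak, the nominal Days 8, 15 and 21 are all inside. An end-of-cycle sample falls outside only when taken late in its tolerance, on Days 23 to 28 of the permitted Day 21 ± 7.
- **Every candidate outside the peak window is misplotted.** This fails when bilirubin near the patient's own peak also exceeds 2×ULN, or when the AST plot recovers the case.

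**Conclusion.** The point holds as a gap in how candidates are identified and reported. Under SAP 4.4.3 a patient can meet the SAP's own ALT and bilirubin limits and still be plotted lower right. This needs a qualifying elevation that is not the peak, bilirubin ≤2×ULN within 7 days of the peak, and no recovery by the AST plot. Separately, the report contains no tabulated joint count whatever the number of cases, and below five candidates the liver table is not produced at all.

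The number of patients affected cannot be computed, because the documents give neither a bilirubin elevation rate nor a Hy's Law rate, and it could be zero. The probabilities for the five-patient condition rest on assumed rates and on a pool that the SAP does not define. The case for change is that the fix is cheap and removes a possible conflict with the SAP's own definition. It is not that a known number of cases is being lost. The SAP already uses an any-time search elsewhere: its capillary leak algorithm (SAP 8.3) can flag a patient on two criteria starting within 7 days of each other, without anchoring to one peak and without a minimum count.

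**What to change.** In SAP 4.4.3:
- Identify candidates by screening every on-study ALT or AST >3×ULN, not only the peak, for total bilirubin >2×ULN in a pre-stated two-sided window.
- Keep at least the current 7 days before the elevation. A same-day-or-later window would lose bilirubin rises just before the ALT elevation that the present rule can catch.
- Extend the window after the elevation to the next cycle's first infusion, or to 30 days after the last infusion if there is no further cycle, and never to less than the current 7 days. For an ALT on Day 21 the present window runs to Day 28, past the next cycle's Day 1, and that reach should not be lost.
- Mark these patients on the ALT and AST plots.
- Delete the five-patient condition and always report the joint ALT/AST-plus-bilirubin count, with concurrent ALP and a stated denominator.

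The cost is SAP wording and one programming change on data already collected. The downside is that a few more patients may be flagged and need narrative review.

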4.4.4. Vital Signs and Physical Examination

The actual value and change from baseline (Day 1) to each on-study evaluation and to the last on study evaluation will be summarized for vital signs.

A summary table of the number and percent of patients with treatment-emergent potentially clinically significant (PCS) vital signs parameters will be tabulated based on the following criteria:

Variable Name	PCS – Low if:			PCS – High if:		
	Observed Value is:	AND	Decrease from Baseline is:	Observed Value is:	AND	Increase from Baseline is:
Systolic Blood Pressure	<90 mmHg		≥20 mmHg	>180 mmHg		≥20 mmHg
Diastolic Blood Pressure	<50 mmHg		≥10 mmHg	>105 mmHg		≥10 mmHg
Heart Rate	<50 bpm		≥15 bpm	>120 bpm		≥15 bpm

PCS= potentially clinically significant.

All tables summarizing vital sign measurements only include visits in which at least 10% of the analysis population had measurements. Vital sign measurements will be presented for each patient in a data listing.

All physical examination findings and ECOG performance status findings will be presented in data listings.

4.4.5. Electrocardiogram

Electrocardiogram results will be summarized descriptively, including the number and percentage of patients with normal, abnormal, and clinically significant abnormal results at baseline and each study visit. Actual values and change from baseline will be summarized for QTc intervals; continuous summary statistics will be based on the mean of the triplicate ECG values, as appropriate. All tables summarizing ECG measurements only include visits in which at least 10% of the analysis population had measurements

Based on 12-lead triplicate ECG results, the number and percentage of patients whose mean QTcF or QTcB value at any time point meets any of the following categories will be summarized:

- >450 msec
- >480 msec
- >500 msec
- increase from baseline >30 msec
- increase from baseline >60 msec

Electrocardiogram and echocardiogram/MUGA data for each patient will be provided in data listings.

4.4.6. Concomitant Medications and Subsequent Treatments

Concomitant medications will be coded using the WHO Drug Dictionary. Results will be tabulated by anatomic therapeutic class (ATC) and preferred term.

Concomitant medications will be tabulated for previously specified safety groups, where any medications that were not discontinued prior to the first dose of study drug will be included. If an end date is missing or the medication is ongoing at the time of first dose, the medication will be considered concomitant.

The use of concomitant medications and subsequent treatment(s) will be included in by-patient data listings.

4.4.7. Pre-Treatment Medications

Pre-treatment medications will be coded using the WHO Drug Dictionary. Results will be tabulated by ATC and preferred term. In addition, the number and percent of patients who receive pre-treatment medication at least once will be summarized for previously specified safety groups.

Pre-treatment medications will be included in by-patient data listings.

4.5. Summary of Immunogenicity Parameters

Immunogenicity parameters will be summarized for FL BPDCN, R/R BPDCN, all BPDCN, Stage 4 (lyophilized formulation) only, and all patients pooled across all doses and stages.

Analyses will be conducted in accordance with the principles outlined in ([Shankar, et al. 2014](#)) and will include:

- Incidence of patients with positive anti-drug antibodies, specific anti-hIL-3 antibodies, and neutralizing antibodies will be assessed by cycle uniquely through cycle 6 and cycles >6 , collectively. Incidence will be summarized by number and percent of patients with positive antibody results.
- Mean fold increase from baseline and geometric mean titer are tabulated by scheduled assessments. Summary statistics will include mean, SD, median, min, and max.
- Incidence of subjects with a ≥ 10 fold increase in anti-drug antibody titer and/or a ≥ 4 fold increase in anti-hIL-3 antibody titer will be tabulated.
- Complete response, objective response, and complete response rates will be tabulated with 95% clopper exact CIs for subjects with a ≥ 10 fold increase in anti-drug antibody titer and/or a ≥ 4 fold increase in anti-hIL-3 antibody titer.
- Descriptive statistics will be provided for the count of AEs, AESIs, Immune-complex related AEs, serious AEs, and AEs leading to Discontinuation by antibody status and the fold increase populations previously described.

Immunogenicity parameters will be included in by-patient data listings.

5. CHANGES TO PLANNED ANALYSES

5.1. SAP Version 1.0 (28 April 2017)

In the Study Protocol (Amendment 9), in Section 12.6.3 Duration of Response is defined as the time from CR to disease progression. In case a patient does not progress, the protocol definition specifies that censoring will occur on the last radiologic assessment while on study. In this SAP [Section 4.3.2](#) (Duration of Response) and [Section 4.3.4](#) (PFS), censoring will occur on the date of last disease assessment, including BM, skin, or radiologic assessments, as appropriate and in accordance with the patient-specific disease presentation.

In the Study Protocol (Amendment 9), in Section 12.6.2 Bone Marrow Complete Response is defined as patients “who had either CR or PR with complete bone marrow response (reduction to <5% blast cells), as a proportion of all patients with marrow disease ($\geq 5\%$ blast cells) at baseline.” Per the response criteria; however complete BM response requires a reduction to $\leq 5\%$ blast cells. This notation was corrected in the SAP [Section 4.3.1](#).

A footnote was added to the Response Criteria for BPDCN from Protocol (Amendment 9) to define marked clearance of skin disease and residual hyperpigmentation or abnormality identified on a biopsy (or no biopsy performed) as quantifiable changes to skin disease for identification of the achievement of CRc. ([Section 8.2](#))

5.2. Changes from SAP Version 1.0 (28 April 2017) to Version 2.0

Changes from SAP Version 1.0 (28 April 2017) include:

- [Section 1.1.3](#): [REDACTED] modification to the Study Protocol and SAP Version 1.0 definition to complete response from CR + CRc + CRi to include only CR + CRc. An assessment of rate and duration of CR + CRc + CRi was added as an exploratory analysis.

In addition, the modification to the definition of CRc, including a quantifiable definition of “marked clearance” and “residual” were added to this SAP.

- [Section 2](#): The population definitions were updated to improve clarity on their implementation in the analysis of the patient data.
- [Section 3.5](#): Additional information was added to the Methods for Pooling Data to clarify the intent and implementation of analysis of the patient data.
- [Section 3.9](#): Subgroup analyses were updated to better describe the analyses to be performed. The list of subgroups were modified to include only those relevant for analysis where at least 10% of patients fall within each group. In addition, the efficacy subgroup analyses were removed since SAP Version 1.0 as the analyses will not be performed.
- [Section 3.14.3](#): The cutoff date for analysis is identified as 25 September 2017 to allow all surviving patients at least 6 months of follow-up.
- [Section 4](#): Corrections and clarification of efficacy and safety analyses were added to the document.

- Corrections were made to exploratory time to event endpoint descriptions and planned analysis methods, including the addition of TTP as an exploratory endpoint.
- Time to event response endpoints of duration of CR, duration of BMCR, duration of OR, PFS, and RFS are censored on the latter of date of last treatment with tagraxofusp or date of last disease assessment prior to data cutoff. ○ In addition to other clarifications, the AESI section is updated for greater detail of the particular events of interest.
- Additional specification of CLS outputs to be included in CSR.

